1.0 Objectives

1.1 Study Objectives

The aim of our study is to evaluate the effectiveness of prazosin in bulimic patients experiencing distressing nightmares secondary to PTSD. We will be testing 10 participants. 8 will be tested using subjective measures (Phase A). If a signal of efficacy is detected the last 2 participants will be tested using additional objective PSG measurements (Phase B). Phase B will be a feasibility study and based on results PI will apply for external funding.

AIMS FOR PHASE A:

The Primary aim of our study is to evaluate the effectiveness of prazosin in bulimic patients experiencing distressing nightmares secondary to PTSD using subjective measures.

Hypothesis 1:

Prazosin is associated with decrease in nightmare frequency in bulimic patients

The secondary aim of our study is to assess changes in Cortisol levels in bulimic patients with PTSD before and after treatment with prazosin.

Hypothesis 2:

Prazosin use is associated with a decrease of cortisol levels.

1.2 Primary Study Endpoints

Primary outcome measure: Decrease in frequency of nightmares (subjective measures)

1.3 Secondary Study Endpoints

Secondary Outcome measures: Decrease in total CAPS score, depressed mood, bulimia symptoms and self-harm thoughts on depression scale

AIMS FOR PHASE B:

Phase B will involve using objective polysomnogram measurements (hypothesis 3) in addition to the subjective instruments used in phase A.

The Primary aim of our study is to evaluate the effectiveness of prazosin in bulimic patients experiencing distressing nightmares secondary to PTSD using subjective measures.

Hypothesis 1:

Prazosin is associated with decrease in nightmare frequency in bulimic patients

The secondary aim of our study is to assess changes in Cortisol levels in bulimic patients with PTSD before and after treatment with prazosin

Hypothesis 2:

Prazosin use is associated with a decrease of cortisol levels.

Hypothesis 3:

Prazosin is associated with decrease in REM density & normalization of REM disruption (objective).

1.4 Primary Study Endpoints

Primary outcome measure: Decrease in frequency of nightmares (subjective measures)
Decrease in REM density on PSG (objective measures)

1.5 Secondary Study Endpoints

Secondary Outcome measures: Decrease in total CAPS score, depressed mood, bulimia symptoms and self-harm thoughts on depression scale

2.0 Background

2.1 Scientific Background and Gaps

Nightmares are a frequent and distressing symptom in patients struggling with post-traumatic stress disorder (PTSD). Up to eighty percent of patients with PTSD experience nightmares which predominantly occur during the REM phase of sleep¹. Some adult studies have also demonstrated association between suicidal ideation or attempt and increased REM sleep². PTSD presents as common comorbidity with eating disorders and traumatic experiences often lead to development of Bulimia nervosa³. According to some studies up to 40 % of women with bulimia nervosa experience PTSD and the frequency is even higher in those with active binging symptoms^{3,4}.

2.2 Previous Data

PTSD has been associated with the etiology, course, and severity of Bulimia nervosa³. Nightmares are frequently reported by patients struggling with bulimia nervosa & PTSD. Clinicians managing patients with bulimia nervosa frequently report that bulimic patients experiencing nightmares have more serious psychopathology. However, little is known about the impact of nightmares on the severity and course of bulimia. Some researchers have posited that treatment resistance in bulimic patients may be secondary to PTSD symptomatology and treatment of PTSD may alleviate bulimic symptoms⁵. However, no studies have explored the impact of nightmares on bulimic symptoms, and whether their presence predicts the course or treatment response in bulimia nervosa. This gap in our knowledge is crucial given the high frequency of PTSD symptoms in bulimia.

Deregulated hypothalamic-pituitary-adrenal axis activity has been reported in both PTSD and Bulimia nervosa but the results of the studies are inconsistent. Some studies in PTSD report hypocortisolism at baseline^{6, 7} while others report that women with higher cortisol responsiveness to stressors tend to eat more during stress. Furthermore, binging and purging symptoms may trigger increased release of cortisol accounting for high cortisol levels in many patients with Bulimia nervosa. Prazosin, an alpha-1 adrenergic receptor antagonist, affects the stress system, including HPA axis. Evaluating the activity of the HPA axis in bulimic patients with PTSD before and after treatment may help us understand the underlying pathophysiology of this disorder and in predicting treatment response in these patients⁸.

Although various psychopharmacological options are being utilized to provide symptomatic relief of nightmares, there is limited scientific evidence about their effectiveness in nightmare management. Furthermore, literature is almost non-existent about therapeutic options for patients with bulimia nervosa experiencing nightmares. Prazosin has been used extensively for treatment of nightmares in PTSD in both civilian and veteran population and has proven to be subjectively and objectively effective^{9, 10}. Reversal of REM sleep disruption has been observed following treatment with prazosin¹¹. Other studies have reported decrease in trauma-related distressing dreams with the use of prazosin, which tend to return after its discontinuation¹¹.

2.3 Study Rationale

To our knowledge, there is no treatment trial for prazosin use in patients with bulimia nervosa struggling with nightmares, looking at either objective or subjective measures. We plan to probe the effectiveness of prazosin in bulimic patients experiencing nightmares due to PTSD using both subjective and objective measures in order to improve future clinical care. The effects of

prazosin on decreasing nightmares and bulimic symptoms on subjective scales and effects on sleep architecture using objective polysomnogram measurements will help inform targeted psychopharmacologic and psychotherapeutic strategies to improve clinical care of bulimic patients struggling with distressing dreams secondary to PTSD. This study will be performed in two phases. Phase A will involve eight participants who will be tested using subjective scales (mentioned below). If Phase A data analysis leads to detection of a signal of efficacy 2 more participants will be recruited to participate in phase B of this trial using objective polysomnogram measurements. The results from this project will aid in establishing a fully powered clinical trial for treatment of nightmares in bulimic patients and improve outcomes in this high risk population.

3.0 Inclusion and Exclusion Criteria

3.1 Inclusion criteria: Women struggling with bulimia nervosa (purging and non-purging type) between 18-45 years of age recruited via physician referrals or advertisement materials with complaints of nightmares secondary to PTSD. Patients may or may not be taking SSRIs and their use will not exclude them from the study.

3.2 Exclusion criteria: Restless leg syndrome, narcolepsy, sleep apnea, currently taking prazosin, neurological disorders, pregnancy, cardiac abnormalities, significant electrolyte abnormalities, use of steroids or Beta blockers and abuse of alcohol or other substance during the past three months(due to their effects on sleep parameters). Prazosin is commonly used to treat symptoms of PTSD and unless cardiac abnormalities are detected at baseline, EKGs are not routinely performed during treatment. We will exclude the patients with cardiac abnormalities from our study if the baseline EKG detects some abnormalities; they will be referred to cardiologist for further follow up. Blood work will be drawn to detect electrolyte abnormalities commonly seen in bulimic patients and patients will clinically significant electrolyte abnormalities will be excluded from the study. Physical examinations will not be performed as these patients follow up at the eating disorder clinic and those data are already available, data from the preexisting medical evaluations will be used to discern any major neurological or other physical abnormalities and participants will be excluded from the study.

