6.3 Waiver or alteration of authorization statements of agreement

7.0 Study Design and Procedures

7.1 Study Design

Study Design: We plan to conduct a 7 week prospective, double blind, placebo controlled crossover study. Each patient, in a randomized design will receive three weeks of prazosin and three weeks of placebo separated by 1 week washout period. A 1-week washout period is considered sufficient, given that the half-life of prazosin is 2-3 hours, and previous studies have demonstrated that the clinical effects of prazosin are eliminated within a week^{10, 11}. The subjects

will be blinded and the randomization list will be sent directly to the research pharmacy. Methylcellulose will be used as placebo.

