11.0 Data and Safety Monitoring Plan

Although prazosin is routinely used in clinical settings in bulimic patients experiencing PTSD and nightmares and thus does not pose more than minimal risk for the patients, the research team will have the following data and safety monitoring plan to ensure safety and prevent any untoward outcomes.

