24.1.6.5 Prior and Concomitant Therapy

Prazosin is the only treatment being offered in this study. Subjects cannot be taking steroids or beta blockers and will be excluded from the study if used.

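### Entry rules do not control recent prazosin use or unstable SSRI use, which can blur the Day 2 baseline and add noise but is not shown to bias the end-of-arm contrast

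*Combined protocol and SAP*

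**What the plan says.** - **SSRIs (Section 3.1):** "Patients may or may not be taking SSRIs and their use will not exclude them from the study". No duration, dose or stability condition follows.
- **Prazosin (Section 3.2):** the exclusion list reads "Restless leg syndrome, narcolepsy, sleep apnea, currently taking prazosin, neurological disorders, pregnancy" and continues with other conditions. Only current use is named.
- **Look-back in the same list:** it also excludes "abuse of alcohol or other substance during the past three months(due to their effects on sleep parameters". The authors did consider earlier exposure, but not for the study drug or SSRIs.
- **Concomitant therapy (Section 24.1.6.5):** "Subjects cannot be taking steroids or beta blockers and will be excluded from the study if used". It is silent on SSRI changes and earlier prazosin.
- **Washout (Section 7.1):** one week between arms, because "previous studies have demonstrated that the clinical effects of prazosin are eliminated within a week".
- **Background use:** Section 11.0 says "prazosin is routinely used in clinical settings in bulimic patients experiencing PTSD and nightmares". Section 2.2 says of trauma-related dreams under prazosin: "which tend to return after its discontinuation".
- **Timing in Phase A (Sections 7.2.1, 7.2.2 and 7.3):** screening is on Day 1. Baseline scales, five saliva samples, randomization and treatment start are on Day 2, with no run-in. Scales are repeated at the end of arm 1, the end of washout and the end of arm 2.
- **Analysis (Section 9.2):** t-tests, and a mixed model with period and sequence terms that adjusts for demographics and baseline measures. No medication covariate is named.

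**The concern.** A crossover relies on each patient being roughly stable apart from the study drug. The protocol takes care of this between arms but not before the first one. By its own account a patient who stopped prazosin shortly before Day 1 may still be under its effect on Day 2, yet that patient is eligible and is measured and started on treatment that day.

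The Day 2 value has three uses. It is the before value for the cortisol aim in Section 1.1, and Section 2.2 says prazosin acts on the HPA axis. It is a covariate in Section 9.2. It is also the starting point for weekly titration by nightmare severity in Section 7.2.3.

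SSRIs raise a separate question. Constant use cancels when a patient is compared with herself. A start, stop or dose change just before or during the 7 weeks does not cancel, and it could move total CAPS, depressed mood and bulimia symptoms (the secondary endpoints in Section 1.3) by different amounts in the two arms.

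**Working it through.** **Step 1. How far residual prazosin can reach.** Take the extreme eligible case: last dose on the day before Day 1, that is Day 0.

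- Effects gone, by Section 7.1: Day 0 + 7 = Day 7.
- Baseline and treatment start: Day 2, inside that window.
- First dose adjustment: about 7 days after the start. It draws on a week that lies mostly inside the window.
- Last day of arm 1: 21 treatment days starting on Day 2 end on Day 22. The margin is 22 - 7 = 15 days.

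Residual effect can therefore touch the baseline and early titration, but not the end-of-arm ratings or saliva.

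**Step 2. The baseline as covariate.** With one baseline per patient, the adjustment term is the same in both arms and drops out of the within-patient difference for anyone who completes both. A contaminated value then distorts change-from-baseline results and the patient's fitted level, but not the prazosin-placebo difference. Section 9.2 does not say whether the end-of-washout rating is to serve as a second baseline. If it were, this cancellation would not be exact.

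**Step 3. Reproduce the planned power.** Inputs from Section 9.1: placebo 6.0 (SD 1.5), prazosin 3.5 (SD 2.5), correlation 0.3, N=10, two-sided alpha 0.05.

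- Difference: 6.0 - 3.5 = 2.5.
- SD of the paired difference: √(1.5² + 2.5² - 2×0.3×1.5×2.5) = √6.25 = 2.50.
- Paired t-test, noncentral t with 9 degrees of freedom, noncentrality (2.5/2.50)×√10 = 3.16: power 80.3%, against the stated 80%.

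All six rows of the table reproduce within 2 points. No planning figure is in dispute.

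**Step 4. Cost of patient-specific drift.** The documents give no size for an SSRI effect, so the drift SD *e* is an assumption. It adds to the variance of the paired difference: SD = √(6.25 + e²). The calculation uses the nightmare item because only that item has planning SDs.

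| Assumed e | SD of difference | Power, N=10 | Power, N=8 |
|---|---|---|---|
| 0 | 2.50 | 80.3% | 68.1% |
| 0.5 | 2.55 | 78.8% | 66.4% |
| 1.0 | 2.69 | 74.3% | 61.8% |
| 1.5 | 2.92 | 67.6% | 55.1% |
| 2.0 | 3.20 | 59.6% | 47.8% |

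To give *e* a scale: if one patient in ten shifts by 2.5 points in either direction and the rest do not shift, e = √(0.1×2.5²) = 0.79. The N=8 column is shown because Phase A has 8 patients and its result decides whether Phase B opens.

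**Step 5. Drift common to all patients.** The period term in the mixed model removes it. The t-tests are not described as adjusting for period. In an unadjusted paired mean, a common drift of D points leaves a bias of D×(n₁ - n₂)/n, where n₁ and n₂ are the numbers in the two sequences. That is 0 with a 5:5 split, 0.2D with 6:4 and 0.4D with 7:3.

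**The case against.** The strongest reply is that the prazosin gap is harmless on the protocol's own premise. If effects are gone within a week, they are gone about two weeks before the first outcome rating, and Section 9.2 centres the analysis on prazosin versus placebo, not on change from baseline. This stands for the end-of-arm contrast. It does not cover the cortisol aim, which is worded as before versus after, or the expectation in Section 9.2 that baseline and placebo will not differ.

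Second, few patients may be affected. Routine use in this population implies current users, who are already excluded, and Section 4.4 requires ongoing nightmares scoring at least 3 on the CAPS item, which works against enrolling someone whose nightmares are still suppressed. Both remarks are fair. They make the case less frequent without closing it, and the documents give no count.

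Third, SSRI drift is not directional. Sequence is randomized (Section 24.1.3), so a change over time enters the treatment contrast with either sign, and the drift may span both periods. This stands, and it is why the cost is expressed as lost precision.

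A reader might instead infer a sizeable bias: two patients each shifted by 2.5 points in the same direction move the mean difference by 2×2.5/10 = 0.50, or 2×2.5/8 = 0.63, which is 20-25% of the planned effect. The documents do not support that reading. The 2.5 points are the whole planned treatment effect reused as a contaminant, the calculation needs matching signs, and the SSRI harm in question falls mainly on the secondary scales, not on the nightmare item.

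**Conclusion.** Both gaps are real. No section sets a prazosin-free interval before baseline or an SSRI stability condition. The statement in Section 24.1.6.5 that prazosin is the only treatment offered describes what the study supplies; it does not hold background medication constant. The prazosin rule is also out of step with the washout reasoning in Section 7.1.

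The consequence is limited. Recent prazosin use can contaminate the Day 2 baseline, and with it the before/after cortisol comparison, the covariate and early titration. It might be tempting to conclude that it carries into the arm-1 outcome; by the one-week premise it does not. Unstable SSRI use mainly costs precision: N=10 power falls from 80.3% to about 79-74% under assumed drift SDs of 0.5-1.0, and no directional bias is demonstrated.

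This rests on the protocol's one-week statement being right, on one baseline per patient, and on assumed drift sizes. How many patients are affected is unknown. Severity: minor.

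**What to change.** - **Section 3.2:** reconcile the prazosin exclusion with Section 7.1, so that the washout period the protocol already uses between arms also applies before baseline.
- **Section 3.1:** admit SSRI users only if the regimen has been stable for an interval the investigators set and no change is planned during the 7 weeks.
- **Data collection:** record the date of any earlier prazosin use and any SSRI change during the study. Changes needed for care are not restricted.

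A sensitivity analysis that drops affected patients is not worth adding: with 8 to 10 patients it would tell little.

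The cost is two eligibility sentences and a medication-date field, with a short entry delay or slightly slower recruitment for a few patients.

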3.3 Early Withdrawal of Subjects

3.3.1 Criteria for removal from study

Safety concerns, failure of subject to adhere to protocol requirements, subject consent withdrawal.

3.3.2 Follow-up for withdrawn subjects

A follow up phone call by the research assistant to provide instructions regarding the medication will be conducted. Patients will be asked to return any unused medication and standard care will be offered to patients if they choose not to participate in the research study or are withdrawn early.

4.0 Recruitment Methods

4.1 Identification of subjects

Subjects will be identified at the Briarcrest eating disorder clinic by a therapist & additionally there will be flyers in the office regarding participation in the study. Study flyers will also be sent to other physicians and therapists in the community. The therapist will screen and identify each subject and obtain verbal consent. After the initial screening, the therapist will inform the RA who will initially get verbal consent and schedule patient for the first day of screening procedures. The physical location of the evaluations will be at GCRC where the psychiatrist will perform the evaluations; however the initial screening by the therapist will take place at the Briarcrest eating disorder clinic.

4.2 Recruitment process

The research assistant will contact the participants to obtain consent and avoid any form of coercion from healthcare providers. The research assistant will get verbal consent via phone and schedule the patient for consent discussion, therapist evaluation (if not already in medical record), the screening lab work, pregnancy test, Salivary Cortisol collection, BMI, Vital signs, CMP, LFTs, UDS & EKG.

Informed consent will be obtained at the GCRC by the Research Assistant.

4.3 Recruitment materials

There will be flyers in the therapist office.

4.4 Eligibility/screening of subjects

The potential subjects will be patients following up in the eating disorder clinic. They will receive initial screening from the therapist who will use the DSM-5 based evaluation that is utilized routinely in the clinic and ascertain the diagnosis of Bulimia nervosa. Patients with co-morbid PTSD with ongoing nightmares (scoring 3 or above on distressing dreams item of the clinician administered PTSD scale (CAP) will be eligible for this study and the therapist will ask the patients whether they would like to be contacted by the research assistant to participate in the study.

5.0 Consent Process and Documentation

5.1 Consent Process

5.1.1 Obtaining Informed Consent

5.1.1.1 Timing and Location of Consent

The consent process will take place in the GCRC before any study related procedures take place.

5.1.1.2 Coercion or Undue Influence during Consent

The PI or therapist providing care to the patient will not be involved in the consent process. The therapist will ask the

patient about their interest in participation in the study and whether they would like to be contacted by the research assistant. The research assistant will explore interest in participation via phone call and later on the written consent from participating subjects will be obtained at the time of the first blood draw. It will be emphasized that subjects do not have to participate. They will also be told that whatever their decision, their current and future care will not be affected.

5.1.2 Waiver or alteration of the informed consent requirement

N/A

5.2 Consent Documentation

5.2.1 Written Documentation of Consent

A member of the research team authorized to carry out the consent process will:

1. Verify that the subject has received a copy of the consent form and had time to review it.
2. Review the consent form with the subject, answering any questions he/she may have.
3. Ask the subject to sign the consent form indicating he/she understands and agrees to study procedures before study procedures begin.
4. Obtain Signatures and give a signed copy of the consent form to the participant for his/her personal records.

5.2.2 Waiver of Documentation of Consent

N/A

Consent – Other Considerations

Non-English Speaking Subjects

N/A

5.2.3 Cognitively Impaired Adults

N/A

5.2.3.1 Capability of Providing Consent

The patients will be adults and will have the capacity to provide consent.

5.2.3.2 Adults Unable To Consent

N/A

5.2.3.3 Assent

N/A

5.2.4 Subjects who are not yet adults (infants, children, teenagers)

5.2.4.1 Parental Permission

N/A

5.2.4.2 Assent

N/A

6.0 HIPAA Research Authorization and/or Waiver or Alteration of Authorization

6.1 Authorization and/or Waiver or Alteration of Authorization for the Uses and Disclosures of PHI

Check all that apply:

- Authorization will be obtained and documented as part of the consent process.
- Partial waiver is requested for recruitment purposes only (*Check this box if patients' medical records will be accessed to determine eligibility before consent/authorization has been obtained*)
- Full waiver is requested for entire research study (e.g., *medical record review studies*)
- Alteration is requested to waive requirement for written documentation of authorization

6.2 Waiver or Alteration of Authorization for the Uses and Disclosures of PHI

N/A

6.2.1 Access, use or disclosure of PHI representing no more than a minimal risk to the privacy of the individual

